3.3 Duration of Participation

The study consists of 3 epochs: screening/washout period (at least 1 week and up to 4 weeks), treatment epoch (16 weeks from screen/washout), and follow up epoch (4 weeks). The screening and washout period will allow for treatment naïve/ new diagnosis LP to undergo evaluation and diagnosis and for treatment refractory to undergo a washout. The total duration of the study will be 21-24 weeks, with the option to enroll in a 3 month extension with a dose escalation to 4 mg for patients who demonstrate response to treatment, but have not yet achieved PGA 0

Tables:

Table-1: Prohibited treatment

Prohibited treatments ^{†,‡}	Washout period (before Randomization Visit)
Any concomitant oral or topical JAK inhibitor	Prohibited
Any biologic drug	Stable dose for 3 months
Immunomodulation treatments for LP§	4 weeks
[e.g., methotrexate, cyclosporine A, corticosteroids (oral, i.v.,	
intramuscular, s.c., intra-articular, transdermal),	
mycophenolate mofetil, azathioprine]	
Topical treatment that is likely to impact signs and symptoms of LP (e.g., pimecrolimus, tacrolimus)	2 weeks
Non-immunosuppressive agents (tetracycline antibiotics & niacinamide)	2 weeks
Prohibited regimen of Topical Corticosteroids (TCS)	
TCS on any location on body (including face, scalp and/or genitoanal area)	2 weeks

[†]If the prohibited treatment is being used during the study for any indication, the subject must discontinue use of the prohibited treatment if he/she wishes to continue in the study.

[‡] In case of undue safety risk for the subject, the subject should discontinue study treatment at the discretion of the investigator/qualified site staff. If the subject received a live virus vaccination during the study, the subject must discontinue study treatment.

§Inhalative CS with only a topical effect (e.g., to treat asthma) are not considered "systemic immunomodulation treatments" and are therefore acceptable as co-medication. Immunosuppressive medication for conditions other than LP will be allowed.

Table 2: Washout Periods for Monoclonal Antibodies (Biologic Drugs)

Brand	Generic Name	Recommended Minimum
Name		Washout (approximately 5 half-lives)
ACTEMRA	Tocilizumab	8 weeks
CIMZIA	Certolizumab pegol	10 weeks
COSENTYX	Secukinumab	16 weeks
DUPIXENT	Dupilumab	12 weeks
ENBREL	Etanercept	4 weeks
HUMIRA	Adalimumab	8 weeks
KEVZARA	Sarilumab	7 weeks
ORENCIA	Abatacept	8 weeks
REMICADE	Infliximab	6 weeks
RITUXIN	Rituximab	6 months
SIMPONI	Golumimab	10 weeks

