- Underlying condition (including, but not limited to metabolic, hematologic, renal, hepatic, pulmonary, neurologic, endocrine, cardiac, infectious or gastrointestinal conditions) which, in the opinion of the investigator, significantly immunocompromises the subject and/or places the subject at unacceptable risk for receiving an immunomodulatory therapy
- Moderate-to-severe renal impairment including patients with estimated glomerular filtration rate (eGFR) <60 mL/min/1.73m²
- Active systemic infections during the 2 weeks prior to randomization (common cold viruses excluded) or any infection that reoccurs on a regular basis.
- Current severe progressive or uncontrolled disease which the investigator renders the subject unsuitable for the trial or puts the subject at increased risk
- Have had any major surgery within 8 weeks prior to screening or will require major surgery during the study that, in the opinion of the investigator would pose an unacceptable risk to the patient.
- Have experienced any of the following within 12 weeks of screening: VTE (DVT/pulmonary embolism [PE]), myocardial infarction (MI), unstable ischemic heart disease, stroke, or New York Heart Association Stage III/IV heart failure.
- Have a history of recurrent (≥ 2) VTE (DVT/PE).
- Have a history of lymphoproliferative disease; have signs or symptoms suggestive of possible lymphoproliferative disease, including lymphadenopathy or splenomegaly; have active primary or recurrent malignant disease; or have been in remission from clinically significant malignancy for <5 years prior to randomization.
- Have had symptomatic herpes zoster infection within 12 weeks prior to randomization.
- Have a history of disseminated/complicated herpes zoster (for example, ophthalmic zoster or CNS involvement).
- ALT or AST >2 x upper limits of normal (ULN); alkaline phosphatase (ALP) ≥2 x ULN; total bilirubin ≥1.5 x ULN; hemoglobin <10 g/dL (100.0 g/L); total white blood cell count <3000 cells/μL (<3.00 x 103/μL or <3.00 billion/L); neutropenia (absolute neutrophil count [ANC] <1500 cells/□L) (<1.50 x 103/□L or <1.50 billion/L); lymphopenia (lymphocyte count <1000 cells/μL) (<1.00 x 103/μL or <1.00 billion/L); thrombocytopenia (platelets <100,000 cells/μL) (<100 x 103/μL or <100 billion/L)
- Have a positive test for hepatitis B virus (HBV) defined as:
 - a. positive for hepatitis B surface antigen (HBsAg), or

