the stimulus. Maximal inhibition of pSTAT3 formation occurred approximately 1 to 2 hours post-dose, coincident with t_{max}. The pSTAT3 levels returned approximately to baseline levels by 24 hours for all dose groups following single and multiple doses. Based on the results from Study JADF and Study JADE, a PK/PD relationship was established for baricitinib-induced inhibition of IL-6 stimulated pSTAT3 formation. The calculated IC50 value was 75 nM (27.9 ng/mL) from Study JADF and 100 nM (37.1 ng/mL) from Study JADE (for a combined value of 90 nM (33.3ng/mL). These results are similar to the IC50 value of 104 nM (38.6 ng/mL) estimated from in vitro data. These data suggest that QD dosing of 4-mg, but not 2-mg, results in a period of time when the baricitinib concentration in the central compartment is above the ex vivo IC50 for IL-6-stimulated pSTAT3 formation.

Pharmacokinetics:

Baricitinib is rapidly absorbed with a median time of maximum observed drug concentration (tmax) of 1 hour (range: 0.5 to 3 hours). Over a single-dose range of 1 mg to 30 mg in healthy subjects, mean estimates of baricitinib Cmax and AUC_(0-∞) increased approximately proportionally to dose. Baricitinib PK after multiple doses were predictable from single dose data. Accumulation during QD dosing was minimal, with an accumulation ratio of 1.11- and 1.15-fold for Cmax and AUC, respectively. Steady state was typically reached between the second and third doses.

Renal elimination of parent is the principal clearance mechanism for baricitinib, and baricitinib apparent clearance (CL/F) is directly related to baseline glomerular filtration rate (GFR). The differences in CL/F between populations are likely due to differences in renal function, which affects apparent renal clearance (CLr/F). Pharmacokinetic parameter estimates are also available for patients with atopic dermatitis based on Phase 2 Study I4V-MC-JAHG (JAHG), although a different PK model was applied. The estimated values of CL/F and apparent total volume of distribution were 12.3 L/h and 105 L, respectively for this patient population.

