Transporters: In vitro, baricitinib is a substrate for OAT3, Pgp, BCRP, and MATE2-K. In a clinical pharmacology study, probenecid (OAT3 inhibitor with strong inhibition potential) dosing resulted in approximately a 2-fold increase in AUC(0-∞) with no change in Cmax of baricitinib. Simulations with diclofenac and ibuprofen (OAT3 inhibitors with less inhibition potential) predicted minimal effect on baricitinib. Coadministration of baricitinib with cyclosporine (Pgp/BCRP inhibitor) or MTX (substrate of several transporters) resulted in no clinically meaningful effects on baricitinib exposure.

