5.5 Prior and Concomitant Therapy

Individuals on stable doses of medications for chronic illnesses will be allowed. Individuals on immunosuppressive agents for LP will not be allowed; however, individuals on stable doses of immunosuppressant for other conditions will be allowed if deemed to be safe by the treating physicians. Additional exclusionary drugs are included in Table-1.

Individuals using Baricitinib (LY3009104) should use topical broad-spectrum sunscreens with a minimum of SPF30, avoid excess sunlight, and wear sun protective clothing.

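### Strong OAT3 inhibitors are not restricted, although the protocol reports that probenecid about doubles baricitinib AUC

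*Combined protocol and SAP*

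**What the plan says.** - **Interaction data (section 5.1).** "probenecid (OAT3 inhibitor with strong inhibition potential) dosing resulted in approximately a 2-fold increase in" AUC, "with no change in Cmax of baricitinib". For weaker inhibitors: "Simulations with diclofenac and ibuprofen (OAT3 inhibitors with less inhibition potential) predicted minimal effect on baricitinib". Ketoconazole, fluconazole, rifampin, cyclosporine and methotrexate are reported to have no clinically meaningful effect on baricitinib.
- **Clearance (section 5.1).** "Renal elimination of parent is the principal clearance mechanism for baricitinib".
- **Prohibited treatments (section 3.3, Table 1).** The rows cover "Any concomitant oral or topical JAK inhibitor", biologics, immunomodulators for LP, topical treatments, tetracyclines and niacinamide, and topical corticosteroids. No row names probenecid or OAT3 inhibitors.
- **Eligibility (section 4.2).** The therapy exclusion refers only to Table 1. The section also says that the investigator may not add exclusions. Subjects with eGFR below 60 are excluded.
- **Co-medication (section 5.5).** "Individuals on stable doses of medications for chronic illnesses will be allowed". The proviso that the treating physicians judge the drug safe applies only to immunosuppressants for other conditions. For further excluded drugs the section points back to Table 1.
- **Dose (sections 1.5 and 5.2).** 2 mg once daily to Week 16, then 4 mg for those who enter the extension.
- **Analysis (section 7.3).** Everyone who receives at least one dose is considered for analysis. No rule deals with a subject whose exposure was raised by another drug.

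**The concern.** This is an omission, not a contradiction. The protocol reports an interaction that doubles AUC, but the sections that site staff use to decide eligibility and co-medication carry no rule for it. Read literally, they admit a subject on stable probenecid and leave the investigator no listed ground to refuse.

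The main stake is patient safety. Such a subject could have about twice the intended AUC for 16 weeks, and again after escalation, with nothing prompting staff to notice. The lesser stake is interpretation: the subject's data would be summarised as 2 mg (or 4 mg) data without a flag.

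The eGFR criterion already limits raised exposure through the renal route, whatever its stated purpose. A drug reported to double AUC has no counterpart rule.

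**Working it through.** **Inputs**
- AUC ratio with probenecid about 2, Cmax ratio 1 (section 5.1). This is an observed result with no raw data in the documents, so it is taken as stated.
- AUC approximately proportional to dose over single doses of 1 to 30 mg, with multiple-dose kinetics predictable from single doses (section 5.1). The doses of 2, 4 and 8 mg lie inside that range.
- CL/F 12.3 L/h (section 5.1). It comes from an atopic dermatitis model and is used only as an illustration; the dose equivalence does not depend on it.
- 12 subjects (section 3.2).

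**Exposure.** AUC = dose / (CL/F), with 12.3 L/h = 12,300 mL/h.

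| Regimen | Calculation | AUC (ng·h/mL) |
|---|---|---|
| 2 mg | 2,000,000 / 12,300 | 163 |
| 2 mg + probenecid | 2 × 162.6 | 325 |
| 4 mg | 4,000,000 / 12,300 | 325 |
| 4 mg + probenecid | 2 × 325.2 | 650 |
| 8 mg | 8,000,000 / 12,300 | 650 |

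If the approximate doubling is taken as a ratio of 1.8 to 2.2 (an assumption), the AUC-equivalent doses are 3.6 to 4.4 mg in the main phase and 7.2 to 8.8 mg in the extension.

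**Limit of the equivalence.** It holds for AUC only. Section 5.1 says that "QD dosing of 4-mg, but not 2-mg, results in a period of time when the baricitinib concentration" exceeds the ex vivo IC50. With Cmax unchanged, 2 mg plus probenecid would still spend no time above that level. The subject does not have the full profile of the higher dose.

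**Safety at the neighbouring doses (section 1.4)**

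| Measure | 2 mg | 4 mg | 8 mg |
|---|---|---|---|
| TEAEs, psoriasis to week 12 | 50.0% | 47.2% | 57.8% |
| TEAEs, atopic dermatitis Phase 3 | 58% | 56% | – |
| TEAEs, lupus | 71.4% | 73.1% | – |
| SAEs, lupus | 10.5% | 9.6% | – |
| Serious infections, lupus | 1.9% | 5.8% | – |
| Interruption for AE, lupus (placebo 10.5%) | 6.7% | 20.2% | – |
| AEs of special interest, atopic dermatitis Phase 2 | 27% (10/37) | 45% (17/38) | – |

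The picture is mixed. The special-interest difference has a Fisher exact p of 0.15, and section 1.4 attributes it mostly to nasopharyngitis and upper respiratory infection. All these comparisons double Cmax as well as AUC, so none transfers directly. The added risk cannot be sized from the documents.

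**Likelihood.** The documents give no prevalence of use. With p the assumed proportion of candidates on a strong OAT3 inhibitor, the chance of at least one among 12 is 1 − (1 − p)^12:
- p = 0.1%: 1 − 0.999^12 = 1.2%
- p = 0.5%: 1 − 0.995^12 = 5.8%
- p = 1%: 1 − 0.99^12 = 11.4%
- p = 5%: 1 − 0.95^12 = 46.0%

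One such subject is 1/12 = 8.3% of the trial.

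**The case against.** The strongest case against concedes the omission and the arithmetic, and disputes the weight.

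- **Rarity.** Only one strong inhibitor is named, and nothing in the documents links LP patients to it. The upper figure of 46% comes entirely from an assumed 5%. This stands; the low end of the range may well be nearer the truth.
- **Accepted exposure.** In the main phase the raised AUC equals that of the 4 mg dose the extension gives on purpose, with a lower peak. Only 4 mg plus probenecid goes beyond any planned AUC, and that needs entry to an optional extension. This stands, and it makes the extension the clearer case for a rule.
- **Reassuring safety data.** Section 1.4 reports no SAE difference between 2 mg and 4 mg through 16 weeks in rheumatoid arthritis, one SAE per group in the first part of the psoriasis study, and up to 20 mg daily for 10 days without dose-limiting toxicity. This limits the likely harm. Against it, section 1.6 describes CPK and lipid rises as dose-related and lists its common adverse events for 4 mg or lower.
- **Other safeguards.** The protocol has laboratory monitoring with interruption and discontinuation thresholds (section 8.1), withdrawal for safety (section 4.4.1), an accrual-suspension rule (section 8.4) and a footnote to Table 1 on undue safety risk. The exclusion for unacceptable risk in section 4.2 concerns underlying conditions. Several of these would act on harm once it appears; none identifies the co-medication or prevents the exposure.
- **The Investigator's Brochure.** It is not among the documents reviewed and may give handling advice. Even so, the eligibility and co-medication sections do not carry the instruction.
- **Interpretation.** The study is for estimation only, so the effect on its results is small. This is agreed.

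**Conclusion.** The concern holds. Nothing in Table 1, section 4.2 or section 5.5 restricts strong OAT3 inhibitors, and following the plan as written admits a subject at about twice the intended AUC: that of 4 mg in the main phase and of 8 mg in the extension, with Cmax unchanged in both. This rests on the reported 2-fold ratio and on approximate dose proportionality. The clinical consequence is unsized, and the probability that any subject is affected depends on an assumed prevalence.

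It is a change that should be made for patient safety because it is specific and cheap. It does not threaten the study's conclusions. Confidence is medium, mainly because the Investigator's Brochure could not be seen.

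**What to change.** 1. Add a row to Table 1: strong OAT3 inhibitors (for example probenecid), prohibited from Day 0 until the last dose, including the extension. The existing footnote, which requires a prohibited treatment to be stopped if the subject is to continue, then covers on-study use.
2. State in section 5.5 that the permission for stable chronic medication does not extend to these drugs.
3. List any on-study use, with dates, beside that subject's Week 16 PGA and safety data. No repeat analysis is needed.

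Diclofenac and ibuprofen need no restriction.

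**Cost.** One table row and one sentence. The case report form must capture co-medication dates, which the data list in section 3.7 does not name, so that may be a small addition. A rare, otherwise eligible subject would be excluded or would have to change medication. Sample size and analysis methods do not change.

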3.1 General Description

This is a single center, exploratory, open-label, single-arm design study of 12 patients. Treatment naïve and treatment refractory patients with LP will be treated Baricitinib (LY3009104). Patients who are non-responders to physician choice standard of care will undergo a washout period and will be enrolled in the study.

Multiple safety studies have been conducted with Baricitinib (LY3009104) (see Safety) and a dose of 2 mg QD is deemed safe. (Investigator's Brochure) We propose a single center, exploratory, open-label, single-arm design study of 12 patients. Treatment naïve and treatment refractory patients with LP will be treated with Baricitinib (LY3009104) for 16 weeks.

Individuals with cutaneous LP will be eligible. Individuals must have 4 lesions at baseline; however, a minimum of 8 lesions which are at least 5mm in diameter is ideal. All lesions will be annotated, photographed, and scored. The rationale for a minimum of 8 lesions is based upon the assumption of a 50% response rate at 2 weeks. With 8 lesions, there would be a less than 1% chance that all 8 lesions would resolve spontaneously. Prior treatment will be allowed; however, a washout period of 2 weeks for topical and 4 weeks for systemic agents is required. At the washout period, individuals will undergo evaluation with a PGA and BSA calculation. The indexed lesions will be photographed, measured, scored, and recorded with Modified CAILS scores as well. The Modified CAILS calculations will be used for the determination of responsive and non-responsive lesions. Additional Pruritus measures using the VRS, VAS, NRSSkindex-16, and LPQOL will be collected at that time.

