3.4 Primary Study Endpoints

Overall response by PGA of skin at week 16.

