3.6 Primary Safety Endpoints

A thorough baseline screening will be followed for all patients and is outlined in Table-2. A detailed list of the methods in which baseline screening will be performed is outlined in Supplemental 2. All blood draws and safety assessments must be performed prior to study treatment administration. Appropriate safety assessments (e.g., evaluation of AEs and SAEs) should be repeated after dosing with study treatment. A physical examination, including general appearance and vital signs, will be performed as indicated in Table-2. If indicated, based on medical history and/or symptoms, additional exams will be performed at the discretion of the investigator. If possible, the same member of the study site staff throughout the study will perform assessments for an individual subject. Information for all physical examinations will be included in the source documentation at the study site. Significant findings that are present prior to the subject signing informed consent will be included in the Medical History. Significant findings made after the signing of the informed consent, which meet the definition of an AE, must be recorded as an AE. Vital signs (blood pressure, pulse, height, weight) will be assessed at each physical examination as indicated in Table-2 (see Supplemental 2 for details on how to acquire vital signs). Whether action needs to be taken to address notable vital signs will be decided by the investigator, considering the overall status of the subject. Laboratory studies will be drawn as indicated in Table-2. Whether action needs to be taken to address notable laboratory values will be decided by the investigator, considering the overall status of the subject. Hematology assessments will be measured at all scheduled study visits specified in Table-2. Serum chemistry will be a comprehensive metabolic and lipid panels that will be measured at all scheduled study visits specified in Table-2.

If the prohibited treatment is being used during the study for any indication, the subject must discontinue use of the prohibited treatment if he/she wishes to continue in the study. In case of undue safety risk for the subject, the subject should discontinue study treatment at the discretion of the investigator/qualified site staff. If the subject received a live virus vaccination during the study, the subject must discontinue study treatment.

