4.4 Early Withdrawal of Subjects

4.4.1 When and How to Withdraw Subjects

- Subject safety issues
- Failure of subject to adhere to protocol requirements
- Disease progression
- Subject decision to withdraw from the study (withdrawal of consent)

Subjects who withdraw from the study for any reason will have their information recorded at the time of withdrawal. At the time of withdrawal, the subject will be considered at the final treatment date and will move into the treatment observation phase (4 weeks). Subjects will not be replaced. Follow up for subjects will continue to follow the normal follow up (Table-2)

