7.3 Subject Population(s) for Analysis

• All-completed population: All subjects that receive at least one dose will be considered for analysis.

Safety and Adverse Events 8

Definitions 8.1

Unanticipated Problems Involving Risk to Subjects or Others (UPIRTSO)

Any unanticipated problem or adverse event that meets the following three criteria:

- Serious: Serious problems or events that results in significant harm, (which may be physical, psychological, financial, social, economic, or legal) or increased risk for the subject or others (including individuals who are not research subjects). These include: (1) death; (2) life threatening adverse experience; (3) hospitalization - inpatient, new, or prolonged; (4) disability/incapacity - persistent or significant; (5) birth defect/anomaly; (6) breach of confidentiality and (7) other problems, events, or new information (i.e. publications, DSMB reports, interim findings, product labeling change) that in the opinion of the local investigator may adversely affect the rights, safety, or welfare of the subjects or others, or substantially compromise the research data, AND
- Unanticipated: (i.e. unexpected) problems or events are those that are not already described as potential risks in the protocol, consent document, not listed in the Investigator's Brochure, or not part of an underlying disease. A problem or event is "unanticipated" when it was unforeseeable at the time of its occurrence. A problem or event is "unanticipated" when it occurs at an increased frequency or at an increased severity than expected, AND
- Related: A problem or event is "related" if it is possibly related to the research procedures.

Adverse Event

An untoward or undesirable experience associated with the use of a medical product (i.e. drug, device, biologic) in a patient or research subject.

Serious Adverse Event

Adverse events are classified as serious or non-serious. Serious problems/events can be well defined and include;

- death
- life threatening adverse experience
- hospitalization
- inpatient, new, or prolonged; disability/incapacity
- persistent or significant disability or incapacity
- birth defect/anomaly

and/or per protocol may be problems/events that in the opinion of the sponsor-investigator may have adversely affected the rights, safety, or welfare of the subjects or others, or substantially compromised the research data.

events.

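### The plan has no rule for scoring an observed Week-16 PGA after other lichen planus (LP) treatment, so such a score can count as baricitinib response

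*Combined protocol and SAP*

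**What the plan says.** **Endpoint.** Section 3.4 defines the primary endpoint as "Overall response by PGA of skin at week 16". The Appendix grades PGA as percentage change from baseline and labels Grade 0 a complete clinical response and Grades 1-3 partial responses. Section 3.4 does not say which grades count as response.

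**Prohibited treatment.** The dagger footnote to Table-1 (Section 3.3) says that a user of a prohibited treatment may remain: "the subject must discontinue use of the prohibited treatment if he/she wishes to continue in the study". Section 3.6 repeats it: "If the prohibited treatment is being used during the study for any indication, the subject must discontinue use of the prohibited treatment". Neither place gives a waiting time or a consequence for scoring. Section 5.5 adds "Individuals on immunosuppressive agents for LP will not be allowed".

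**Before baseline.** For the same kinds of drug, Section 3.1 states that "a washout period of 2 weeks for topical and 4 weeks for systemic agents is required".

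**Withdrawal.** Section 4.4.1 lists disease progression among the reasons, and also "Failure of subject to adhere to protocol requirements". A withdrawn patient is not replaced and enters a 4-week observation phase. The same paragraph then says "Follow up for subjects will continue to follow the normal follow up", with a reference to Table-2.

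**Analysis.** Section 7.3 says "All subjects that receive at least one dose will be considered for analysis". Section 7.2 offers a mixed model if data are missing at random, with last observation carried forward as a sensitivity analysis.

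**The concern.** The gap concerns scores that are observed, not scores that are missing. The protocol protects the baseline assessment from earlier LP treatment for 2 or 4 weeks, but gives the Week-16 primary assessment no matching protection. A patient whose disease improved because of another LP therapy can then be tallied as responding to baricitinib.

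The likely direction is upward, because most of Table-1 consists of treatments barred for their possible effect on LP. In a single-arm study, no comparison group absorbs the error. Section 7.2 says the study is for estimation only, and Sections 7.1 and 7.2 say its effect sizes will be used to plan later studies. What is at stake is bias in that estimate, not a false-positive test.

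**Working it through.** The plan gives no response rate and no rate of prohibited-treatment use, so there is no figure of its own to reproduce here. The check sets the provisions side by side and then sizes the effect.

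**Step 1: prohibited treatment.** Suppose a patient uses a topical LP treatment and stops it at Week 15. The footnote lets the patient continue, and the Week-16 PGA is taken one week later. Before Day 0, the same drug would have required 2 weeks. Applying the protocol's baseline periods to the primary visit:
- topical agents: 16 - 2 = about Week 14
- systemic agents: 16 - 4 = about Week 12

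Use after those times falls inside the interval that the protocol applies at baseline. Visits carry a 3-day window either way (Table-3).

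**Step 2: withdrawal for progression.** Section 4.4.1 can be read in two ways.
- *The visit schedule governs.* Sections 3.6 and 8.1 use the label Table-2 for the schedule of assessments, although the schedule is printed as Table-3 and the printed Table 2 lists biologic washouts. On this reading, a patient withdrawn at any time can have a Week-16 PGA.
- *The 4-week observation phase governs.* Section 4.4.2 repeats the 4 weeks, and Section 3.3 gives the follow-up epoch the same length. On this reading, only withdrawal at about Week 12 or later (12 + 4 = 16) can give a Week-16 PGA.

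**Step 3: does any analysis rule catch the score?** The mixed model and last observation carried forward act on missing values. A recorded PGA is not missing. Section 7.3 considers the patient, and Section 3.4 attaches no condition about treatment. Nothing reclassifies, sets aside or flags the score.

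**Step 4: size.** Take n = 12 (Section 3.2) and response as PGA Grades 0-3 (an assumption). Each reclassified patient moves the proportion by 1/12 = 8.3 points. The table assumes that six responders are observed, and gives exact (Clopper-Pearson) 95% limits: the 0.025 quantile of Beta(x, n - x + 1) and the 0.975 quantile of Beta(x + 1, n - x).

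| Responders owed to other therapy | Proportion | 95% CI |
|---|---|---|
| 0 | 6/12 = 50.0% | 21.1 to 78.9 |
| 1 | 5/12 = 41.7% | 15.2 to 72.3 |
| 2 | 4/12 = 33.3% | 9.9 to 65.1 |

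**Step 5: how likely is at least one affected patient?** The rate r is unknown. With 1 - (1 - r)^12:
- r = 5%: 46%
- r = 10%: 72%
- r = 20%: 93%

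These are chances that at least one of 12 patients receives such treatment. The chance that one also crosses into Grades 0-3 because of it is lower.

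**The case against.** **The plan is silent; it does not direct a wrong result.** A reader might infer that the plan requires these patients to be recorded as responders. It does not. Section 7.3 says dosed patients will be considered, not how a score after other treatment is classified. LP therapy after withdrawal is also hypothetical: the documents neither provide for it nor bar it. This stands, and the point is limited to what can happen under the rules as written.

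**There are partial safeguards.** Section 5.5 bars immunosuppressants for LP, and non-adherence is a reason for withdrawal. But the withdrawal reason is not tied to Table-1 drugs or to response status, and a withdrawn patient is still followed and considered for analysis.

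**Withdrawn patients may have no Week-16 score.** A reader might infer that every withdrawn patient stays on the full schedule. Section 4.4.1 does not settle this. On the 4-week reading the withdrawal route is narrow. A patient who worsened would also have to reach at least 50% better than baseline within about four weeks. The prohibited-treatment route is unaffected.

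**A washout period is not proof of effect.** A reader might infer that a drug taken inside its window is still acting at Week 16. Entry washouts are precautionary and do not show that. They supply only a ready-made, prespecified standard.

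**Using observed values is a legitimate strategy.** It is, if stated. The plan states no strategy, and in an uncontrolled study the observed-value result describes baricitinib plus whatever followed.

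**The study is small and descriptive.** An 8.3-point shift is well inside an interval of 21.1% to 78.9%, and any patient who changes category moves the result by that much. This limits the importance of the point, but wide intervals do not remove a shift in one direction.

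**Conclusion.** The concern holds as a gap in the scoring rules. An observed Week-16 PGA that follows other LP treatment can enter the primary result as baricitinib response, because the continuation, follow-up, population and missing-data provisions together leave it untouched. For withdrawn patients, the extent depends on which statement in Section 4.4.1 governs: any withdrawal on one reading, withdrawal from about Week 12 on the other.

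The size is 8.3 points per affected patient. This assumes 12 patients in the denominator and Grades 0-3 as response; with a stricter cut-off the step is the same, but fewer patients would cross it. The documents give no frequency, so they do not support any claim that the response rate will be inflated by a particular amount. The gap should be closed before data are seen, since a choice made later could turn on one or two known patients. It does not undermine the study as a descriptive pilot.

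**What to change.** In Sections 3.4 and 7.2, state which PGA grades count as response and add a scoring rule. Whatever the observed PGA, count as a Week-16 non-responder:
- any patient withdrawn from baricitinib for progression before Week 16
- any patient who took a Table-1 treatment given for LP, or a topical or systemic agent likely to affect LP signs, within 2 weeks (topical and other 2-week rows) or 4 weeks (systemic immunomodulators) before the Week-16 visit
- for the JAK-inhibitor and biologic rows, which give no usable period, any patient with new use after Day 0

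Do not apply the rule to permitted stable medication for other conditions, or to short courses of non-immunosuppressive agents for an unrelated indication. Without these exemptions, the footnote's any-indication wording would turn genuine responders into failures.

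Flag secondary values recorded after such treatment, and report the observed-value result as a sensitivity analysis. Reconcile the two follow-up statements in Section 4.4.1, and correct the table reference.

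The rule affects scoring only and does not change which treatments a patient may receive. The cost is a few sentences, and possibly a data-collection change. The CRF contents in Section 3.7 do not name concomitant medication, so confirm that start date, stop date and indication are captured. The downside is that the response rate may be slightly lower and an occasional genuine responder may be scored as a failure, which the sensitivity analysis would show.
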